Larger Impact of the Project: Compared to Usual Care, we anticipate that the Integrative Care approach will improve patient satisfaction and reduce safety risks. Both of these will translate to better emotional and physical outcomes, fewer complications and readmissions. Moreover, higher patient satisfaction lessens the number of risk management episodes and substantially reduces the number of malpractice suits.²³ Moreover, the effects on the hospital system could be significant as we can help identify patient safety concerns, optimize care processes and potentially reduce the need for medical services during recovery. From a global perspective, this study is directly aligned with the missions of the Affordable Care Act, and the findings may help improve care processes to meet the federal standards. It is the hope that the processes we propose here can help UF achieve the quality of care metrics that are important to the patient and to the federal agencies that support this institution.

5. Specific Aims:

Specific Aim 1: Determine whether Usual Care or Integrated Care is most efficacious with respect to producing better functional QOL in patients receiving care for orthopedic trauma injury.

Hypothesis: Based on our preliminary findings and others,^{8,24,25} we hypothesize that Integrated Care will be more effective in producing better post-treatment functional QOL than Usual Care.

Specific Aim 2: Determine whether Usual Care or Integrated Care is most efficacious with respect to producing better emotional well-being in patients receiving care for orthopedic trauma injury.

Hypothesis: Based on our preliminary findings and others,^{8,24,25} we hypothesize that Integrated Care will be more effective than Usual Care in producing greater emotional well-being after hospital discharge. This hypothesis is based on our work^{8,26} and others^{4,24,27} that demonstrate lower prevalence and severity of psychological distress with Integrated Care approaches compared to Usual Care in patients with orthopedic trauma.

[figure not shown]
Specific Aim 3: Compare the prevalence of medical complications, rehospitalizations and comorbid disease out to six months after discharge.

Hypothesis: We hypothesize that the Integrated Care group will have fewer rehospitalizations, medical complications and comorbid disease will be present in the Integrated Care group compared to Usual Care. Satisfaction with medical care will be higher in the Integrated Care group.

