The prevalence of medical complications, rehospitalizations and comorbid disease will be captured in two ways: 1) using data extraction methods from the electronic medical records, and 2) directly from patients during their follow-up visits in the outpatient clinics. The number of readmissions (and length of the readmissions), reasons for readmissions, the number and type of complications will be collected. The onset of new comorbid diseases, with particular emphasis on psychological illnesses, will also be collected using these following tools that have been validated for use in the trauma population:

- **The Posttraumatic Stress Disorder (PTSD) Checklist** will be administered to measure posttraumatic stress levels. The PTSD Checklist has high temporal and internal consistency and high content validity.⁴⁹
- **The Beck Depression Inventory-II**²⁹ is a broadly-applicable, clinically relevant psychometric instrument with high reliability and consistency.⁵⁰ BDI-II has high capacity to discriminate depressed and non-depressed people.⁵⁰
- **The State-Trait Anxiety Inventory (STAI)** will be used to measure state anxiety (anxiety about an event) and trait anxiety (anxiety level as a personal characteristic). Internal consistency ranges from 0.86 to 0.95, with considerable evidence of the construct and concurrent validity of STAI-II.⁵¹ STAI values correlate with negative outlook of self and their current experience after traumatic injury.⁵²
- **Pain-Related Fear:** Kinesiophobia is the psycho-social, somatosensory neuronal feedback, manifestation of fear of movement due a belief it will induce pain or injury.^{53,54} To assess the pain-related fear in orthopaedic trauma the Tampa Scale of Kinesiophobia-11 (TSK-11) will be used ($\alpha=0.79$, $ICC=0.81$).⁵⁴

6. Research Quality: Exit Survey about patient perceptions of research and subject interactions.

We hypothesize that the Integrated Care group (with the Transform 10 Program) will have fewer rehospitalizations, medical complications and comorbid disease will be present in the Integrated Care group compared to Usual Care.

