categorical study variables and demographics (means and standard deviations for continuous variables, frequencies and percentages for categorical variables). Chi-square for frequency distributions will be used for patient satisfaction to test main effects of time and treatment and their interaction, on patient satisfaction; however, because patient satisfaction will only be measured at the end, a standard general linear model will be used. The primary analyses for all aims will utilize a mixed model repeated measures approach. These analyses can assess the main effects of treatment and time on outcomes, as well as their interaction (treatment x time). Specifically, independent variables will include care approach (integrated vs standard) and time point (admission, 2 weeks, 6 weeks, 3 weeks, month 6, and 12 months). Dependent variables will include all functional measures (actual and perceived). Mixed models are the preferred approach to analyze data with repeated measures; these models can account for correlation among repeated measurements, flexible time effects, and can handle missing data. Significant interactions between treatment and time would indicate that the change in the outcomes (i.e. slope) was dependent on the patient's treatment group. If a significant interaction is identified, the Preacher method will be used to estimate the magnitude and direction of the interaction. A p value will be established *a priori* at <0.05 for all statistical tests. Continuous data that are not normally distributed will be transformed prior to analysis. Appropriate multiple testing corrections will be performed to limit Type I error.

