Sample Size: A sample size of 100 was determined in an *a priori* manner using G*Power software program.^{55,56} Anticipating that the study population will be younger but otherwise similarly distributed as that of Zimmerman et al.⁴² the sample size, N=100, was determined to be sufficient to have a medium effect size (Cohen's $d=0.60$, power of 0.80, and alpha of 0.05). This then translates into variable detectable mean differences depending on the outcome. For example, a 6.4 point difference in the State Trait Anxiety Index (STAI; one of the psychological measures for the study) can be detected assuming a standard deviation (SD) of 10.0; for AROM a 8.3 difference with an 12.0 SD. Linear mixed effects models will be used to analyze differences between UsCare and ICare in continuous outcomes.⁵⁷ Fixed effects will include randomized treatment group, time of measurement, baseline measurement, and covariates. An interaction term between treatment group and time will be modeled to assess how longitudinal changes in the outcomes differ between treatment groups. Subject-specific effects (random effect) will also be modelled to account for intra-individual correlation across measurement occasion. For categorical outcomes, a similar approach will be employed using generalized linear mixed models with a logit-link function (i.e. mixed-effects logistic regression). Sensitivity analyses will compare the impact of different covariance structures underlying the repeated measurements (e.g. unstructured, autoregressive,⁵⁸ and compound symmetry) on the results from the mixed-effects models.

7. Possible Discomforts and Risks:

Consent: Written informed consent will be obtained after explanation to participants about all procedures and time commitments. The team members will explain to prospective participants the purpose, methods and extent of the study. Potential participants will be asked to read the informed consent form and to ask questions.

Confidentiality: There is the potential minor risk of breach of confidentiality of information

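### Aim 3 concerns events by six months after discharge, but the admission-to-12-month repeated-measures model assigned to all aims does not report that quantity

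*Protocol*

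**What the plan says.** **The aim.** Protocol, Specific Aims, Aim 3: "Compare the prevalence of medical complications, rehospitalizations and comorbid disease out to six months after discharge". The hypothesis predicts fewer of these in the Integrated Care group. It gives no rate and does not say whether it counts patients or events.

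**The model.** Protocol, Statistical Analysis, and the SAP in the same words: "The primary analyses for all aims will utilize a mixed model repeated measures approach". The independent variables are care approach and "time point (admission, 2 weeks, 6 weeks, 3 weeks, month 6, and 12 months"). What is tested is the two main effects and their interaction. The dependent variables named there are the functional measures; the Aim 3 events are not named.

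**The extension to categorical outcomes.** Protocol, Sample Size: "Fixed effects will include randomized treatment group, time of measurement, baseline measurement, and covariates", together with a group-by-time interaction and a subject-level random effect. Then: "For categorical outcomes, a similar approach will be employed using generalized linear mixed models with a logit-link function". The SAP, which carries an earlier date than the protocol, does not contain this sentence.

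**The data.** Protocol, Medical Complications, Rehospitalizations and Comorbid Disease: "The number of readmissions (and length of the readmissions), reasons for readmissions, the number and type of complications will be collected". On comorbidity: "The onset of new comorbid diseases, with particular emphasis on psychological illnesses, will also be collected", using the listed questionnaires. Event dates are not in the list. No questionnaire score is set as marking the onset of disease; the one-standard-deviation rule elsewhere in the protocol triggers a referral.

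**Status.** The Abstract lists these outcomes among the secondary measures.

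**The concern.** A repeated-measures model describes an outcome that has a value at every visit. Aim 3 asks how many patients in each arm have had an event by a fixed date. Three things do not fit when the stated model is applied to readmissions and new comorbid disease:

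1. Nobody can have been readmitted, or have a comorbidity that is new since injury, at admission. That level is zero in both arms.
2. The 12-month level lies beyond the six-month window, and the plan does not say how data from months 6 to 12 enter Aim 3. The model's clock also starts at admission, while the aim's starts at discharge.
3. The odds of an event at a visit are not the proportion of patients with any event by six months.

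At stake is what gets reported for a specific aim with a directional hypothesis. The event coding (new since the last visit, ever by that visit, yes/no by month 6, or a count), the window and the contrast would all have to be settled after the data are in.

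Item 1 does not apply to in-hospital complications or to comorbidity already present at admission.

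**Working it through.** **Plan's own figure.** There is none for Aim 3. The sample size of 100 rests on d = 0.60 for a continuous outcome: n per arm = 2(1.96 + 0.842)²/0.60² = 43.6, so 44 per arm, or 45 by the t test (90 in all). One hundred is therefore sufficient for that purpose, but it says nothing about event outcomes.

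**Step 1: the admission level.** With group, time and group-by-time in a logit model, the treatment log odds ratio at level k is

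L_k = log[a_k/(n − a_k)] − log[c_k/(n − c_k)],

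where a_k and c_k are the event counts in the two arms. At admission a = c = 0, so both logs are minus infinity and L is undefined. An effect averaged over all K levels, (1/K)ΣL_k, contains that term.

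Illustration with invented counts: 50 per arm, 0 and 0 at admission, then 5, 4, 4, 4 (Usual Care) and 2, 2, 3, 2 (Integrated Care) at four visits, fitted by ordinary logistic regression.

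| Iterations | SE, admission-level log OR | SE, average over 5 levels (about 1/5 of it) | SE, last-visit log OR |
|---|---|---|---|
| 8 | 19.9 | 4.0 | 0.890 |
| 12 | 147 | 29.4 | 0.890 |
| 16 | 1,088 | 217.6 | 0.890 |
| 20 | 8,039 | 1,608 | 0.890 |

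The last-visit value can be checked by hand: √(1/4 + 1/46 + 1/2 + 1/48) = 0.890. The first two SE columns never settle. A random intercept adds no events at admission, so the empty level remains in the mixed version. A baseline covariate equal to zero for everyone is constant and drops out.

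**Step 2: the window.** If the last level is taken as reference, the treatment term is finite. In the plan's list that level is 12 months, which is outside Aim 3.

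**Step 3: coding changes the quantity.** Assume Usual Care risks of 10, 6, 5, 5 and 5% in the intervals ending at 2, 6 and 12 weeks and 6 and 12 months, halved under Integrated Care through month 6.

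- Ever by month 6: 1 − 0.90×0.94×0.95×0.95 = 23.6% vs 1 − 0.95×0.97×0.975×0.975 = 12.4%, a difference of 11.2 points. This is the Aim 3 quantity.
- New in the month-6 interval: 5.0% vs 2.5%, a difference of 2.5 points.
- Ever by month 12: 27.5% vs 16.8% (10.7 points) if the effect stops at month 6, or 27.5% vs 21.2% (6.3 points) if the Integrated Care risk in months 6 to 12 is 10%.

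The six-month answer is the same in all these cases; the other figures answer different questions.

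**Step 4: precision of the direct comparison.** Half-width = 1.96√[p₁(1−p₁)/n + p₂(1−p₂)/n], with assumed rates and equal allocation.

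| Assumed rates | 50 per arm | 40 per arm with six-month data |
|---|---|---|
| 20% vs 10% | 1.96√0.005 = 13.9 points | 15.5 points |
| 30% vs 15% | 1.96√0.00675 = 16.1 points | 18.0 points |

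**The case against.** **The model may not be meant for these events.** The list of time levels is followed by a sentence naming only functional measures as dependent variables, so applying admission and 12 months to readmissions is an inference. That is fair, but the plan says all aims and the Sample Size section covers categorical outcomes. If the events do fall outside the model, Aim 3 has no stated analysis, and the same sentences are needed.

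**The empty admission level is harmless.** In part this stands. In a main-effects model of the Step 1 data the treatment SE is stable at 0.425, and with the last visit as reference only the admission terms diverge. If admission served purely as the baseline covariate, the problem would reduce to a constant. But the plan lists admission as a time level and includes the interaction, so the all-visit average has no finite estimate and the finite reference term is the 12-month effect.

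**The model can yield the six-month risk.** True. Month 6 is a level, and the random effect estimates clustering within patients. For example, with visit risks of 5.0% vs 2.6% in four intervals, the six-month difference is 8.7, 7.8, 6.2, 5.2 or 4.5 points at random-intercept SDs of 0 to 4. So a reader should not infer that the model is incapable of a six-month comparison. What is missing is the coding and the contrast.

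**Two further readings go too far.** One is that the plan has no model for binary events, or would analyse them linearly; the Sample Size section names a logit mixed model. The other is that power is lost. In simulation with 50 per arm, the visit-averaged treatment effect had 48% power and the per-patient test 44% for 30% vs 15%, and both had 31% for 20% vs 10%.

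**Prevalence may not be the intended measure.** The aim says prevalence, but the hypothesis can also be read as counts of events, and counts are collected. This stands, and the fix allows for it.

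**Conclusion.** The concern holds as a mismatch between a stated rule and the aim it serves. Taken literally for readmissions and new-onset comorbidity, the model includes a level that cannot be estimated and a level outside the window, and it reports visit-level odds in place of the six-month prevalence that Aim 3 names. The remedy is cheap because the events are already collected.

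The weight is modest: the outcomes are secondary, no loss of power is shown, and a month-6 contrast could be derived under cumulative coding. The conclusion itself depends on no assumed rate. The illustrations and the precision of about ±14 to ±16 points do; they rest on invented rates and on 50 per arm, as the allocation ratio is not stated. That precision is too low for a confirmatory claim unless the difference is very large.

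**What to change.** In the protocol's Statistical Analysis and Sample Size sections and in the SAP:

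- Exempt the Aim 3 event outcomes from the repeated-measures model.
- Compare, per patient, the proportion with any readmission, any complication and any new comorbid disease by six months after discharge, each as a risk difference with 95% confidence interval. For dated, record-based events (readmissions, complications) use the Kaplan-Meier six-month risk when follow-up is incomplete; the Usual Care description lets follow-up depend on the patient's care plan.
- Report between-arm counts of readmissions and complications as a supplementary analysis, since the hypothesis can be read that way.
- Define new comorbid disease, either as a recorded diagnosis or by a questionnaire cut-off set in advance.
- State whether complications before discharge count, and that 12-month figures are supplementary.
- Record event dates.
- Present Aim 3 as estimation.

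The cost is a few sentences and one added data item, the event date. The drawback is that a yes/no comparison ignores repeat events, which the supplementary counts partly cover, and precision stays low at this sample size.

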patients feel better about their physical function and emotional well-being. We believe that patients will feel better about their physical function and emotional health with the Integrated Care approach over the long-term.

Study Description: Usual Care will follow all the highest standards for injury treatment. Integrated Care will include medical care and emotional support. Study Staff are trained to provide emotional support and teach patients the skills for goal setting, taking ownership of journey, establishing lifelines, mobilizing resources and reducing stressors. Questionnaires and hand grip strength will be collected at the hospital and at normal follow-up visits at weeks 2, 6 and 12 and months 6 and 12. Range of Motion will be collected starting at the 2 week follow up visit.

Study Population: Patients who come to the University of Florida Trauma Center for a serious musculoskeletal injury will be asked to participate. A total of 100 people, aged 18-85 years, who have received or will receive ≥ 1 surgical procedures for their orthopedic injuries, will be included. Any major bone fractures that impair mobility and/or participation in activities of daily living and self-care will also be included. Patients may not have a brain injury and may not be using medicines to control psychological illness.

Primary and Secondary Measures: The main study measures are the Patient-Reported Outcomes Measurement Information System (PROMIS) questionnaires of Physical Functional quality of life and Emotional Well-being. Secondary measures are functional measures (Lower Extremity Gain Scale, handgrip strength, range of motion of major joints) and psychological illness questionnaires, medical complications, rehospitalizations, and comorbid disease.

Analytic Methods: We will use specific tests to find out the differences between Usual Care and Integrated Care on our emotional well-being and functional outcome, and adjust results appropriately for missing numbers. Tests will be used to make sure that the study population represents other trauma populations. Participants will repeat all measures at outpatient follow-up visits during weeks 2, 6 and 12 and months 6 and 12.

4. Background:

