Randomization Process: The randomization process will be performed using a random number table and recorded separately into sealed envelopes. These envelopes will be randomly placed into patient folders. After the informed consent process, facilitator will open the randomization envelope. The patient will not know what group they have been randomized to, only the facilitator and study staff will know which group the patient is in. . .

Facilitators: The facilitators are an integral part of the study team. They have all of the proper training (IRB, HIPPA, NIH, etc.) to work with patients in health care and research settings. The Facilitators will be responsible for administering the surveys to collect the data on emotional well-being. The facilitators will also be familiarized with administering the *Transform-10* Program. The facilitators are supervised by the attending orthopaedic trauma physician ([name] or [name]), [name], and a clinical psychologist, [name]. [name], Drs. [name] and [name], and [name] will also serve as mentors for the facilitators as questions arise regarding the implementation of the *Transform-10* Program. The facilitators will make daily rounds with the trauma physician and other daily visits during the patients' hospital stay to ensure they are adhering to their treatment plan and to clarify any details about the patient's injury or treatment plan. The facilitators will serve as liaisons between the hospital staff, physician, clinic staff, and discharge planner. These individuals will be in daily communication with the study team, physician, and/or other hospital personnel to ensure patient safety and that the patients' medical questions are presented back to the attending physicians. Daily monitoring of facilitators by the attending orthopaedic trauma physician and study team will occur via morning conference prior to meeting with patients and a debriefing with the study coordinator at the conclusion of each day.

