Through the use of a centralized folder, the *Transform-10 Program* will include information regarding emotional well-being, social support, and provides opportunity for the patient to openly discuss their thoughts and concerns regarding their recovery. The steps will initially be reviewed with the patient by the Facilitator(s) on the trauma floor at the hospital as it is convenient for the patients. If the patient is alert and willing to review the steps, the facilitator will spend about 10-30 minutes with the patient depending on the patient's questions, concerns, and physical state. Not all steps will be reviewed at one time. The facilitators will be aware of the patient's state and timing of delivery of the *Transform-10 Program*. The goal is to review steps 1-7 during the patient's hospital stay and the remaining steps will be covered at follow-up visits with the physician. If steps 1-7 cannot fit into the patient's hospital stay, these steps will simply be covered at follow-up visits. If previous steps covered during the hospital stay need to be reviewed, the steps will be reiterated at follow up visits. The patient's normal clinical care usually includes a hospital stay, a 2 week follow up, 6 week follow up, 12 week follow up, 6 month, and 1 year follow up visit. Therefore, these steps will be covered over the time of their recovery and care plan. Lastly, patients within this group will receive a structured, physician-approved exercise program at follow-up visits to promote movement and strength prior to beginning supervised physical therapy. The steps of the *Transform-10 program* are shown in Table 1 below^{30-35,27,36-38}.

Table 1. Integrated Care (*Transform-10 Program*): A communication-focused program of ten key steps to personal transformation after orthopaedic trauma.

Step	Process
1. Become a survivor	Move from a mindset of being a "victim" to one of being a survivor; express feelings about trauma and move forward positively.
2. Go all out for recovery	Find things that you are grateful for and appreciate goodness in others and oneself; think of this time as an opportunity to self-improve. Make your environment safe around you while you recover.

3. Movement is life	Conscious thought about and participation in motion improves recovery; celebrate progress in any motion, no matter how small or large. Higher mobility levels are related to greater societal participation and QOL. Better function improves physical safety during recovery.

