4. Set goals for recovery	Contemplate the question, " What gives my life meaning? " Break up the rehabilitation process into small increments to make the recovery process manageable, measurable and controllable.
5. Take ownership of your journey	Seize responsibility and take charge of your recovery to achieve goals. This provides daily purpose and increases self-efficacy. Develop resilience. Draw a 'care map' for you and your recovery. Adhere to safety plans from your doctor.
6. Establish lifelines with others	Use the "buddy system". Rely on a non-family member to be an objective soundboard to help deal with possible physical and psychological setbacks.
7. Mobilize all resources	Mobilize and access free resources. Sunlight, fresh air and free outdoor activities (stage-appropriate exercise) are essential to helping the body and mind recover from trauma.
8. Rally your social support	Bring family and friends together to assist in recovery.
9. Take steps to return to normal	Keep life activity patterns (sleep, diet, exercise) and body rhythms as close to normal as possible.
10. Reduce available stressors	Replace avoidable stressors with positive thoughts and activities such as mindfulness, relaxation and imagery reduces flashbacks and stress.

Data collection and Measurements: The study team will follow a systematic process for data collection. Each patient will have a folder of electronic case report forms on the REDCap repository. Form design will follow *Good Clinical Practice* rules. Within each patient folder, there will be a study checklist. When electronic case report forms are completed, REDCap updates the status to indicate 'completion'. Data will be validated at the time of input by computerized controls that ensure the validity and quality. REDCap contains system integrity measures to guarantee the integrity of the system and to protect against data loss. On a weekly basis, all records will be reviewed by the Facilitators and the Clinical Coordinator.

Patient-Reported Outcomes. Patient-reported outcomes will be primary measures of the study. Patients are the most important source of information regarding the outcomes of interest, because this study focuses on patient perceptions of functional QOL and emotional well-being. At study entry, all patients will be asked to complete surveys with a Facilitator. The combination of proposed subjective and additional objective measures will create a complete picture of the patient experience.

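### Admission is both an outcome visit and a baseline covariate in the mixed models, and no between-arm contrast is named to decide Aims 1 and 2

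*Protocol*

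**What the plan says.** In the Protocol (Research Plan, Statistical Analysis) and in the SAP, the primary analysis for all aims is a repeated-measures mixed model. Its independent variables are care approach and "time point (admission, 2 weeks, 6 weeks, 3 weeks, month 6, and 12 months"). Admission is thus one of six outcome occasions, and no baseline covariate is listed.

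The Protocol's Sample Size section describes the between-arm mixed model differently: "Fixed effects will include randomized treatment group, time of measurement, baseline measurement, and covariates", plus a group-by-time interaction and a subject random effect. It does not say that admission then leaves the time factor. The SAP has no such sentence.

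Both documents say the model can assess treatment, time and their interaction. Only the interaction is interpreted: "Significant interactions between treatment and time would indicate that the change in the outcomes (i.e. slope") depended on the arm. A significant interaction is to be followed by the Preacher method.

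The hypotheses concern levels after treatment. Aim 1 expects that "Integrated Care will be more effective in producing better post-treatment functional QOL than Usual Care", and the abstract expects benefit "with the Integrated Care approach over the long-term". Neither document links these statements to a visit, an average over visits or a change.

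The visit list gives 3 weeks where the abstract, Research Design and the Integrated Care section all have week 12. According to the abstract, range of motion is first measured at the 2-week visit.

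**The concern.** Randomisation should make the arms equal at admission on average. If admission is an outcome and the treatment main effect is read as the result, a visit with an expected difference of zero is averaged in. The estimate shrinks, and the admission score is not used to reduce variance.

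If admission is only a covariate, a benefit that appears by week 2 and then stays constant produces no treatment x time interaction among the follow-up visits. An analyst who combines the Sample Size model with the Statistical Analysis section's focus on the interaction could miss a real, sustained benefit.

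The same data can therefore support different conclusions, depending on a model and a test that neither document fixes. That leaves room for a choice made after the data are seen.

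**Working it through.** **The plan's own figure.** The Sample Size section gives N=100 for d=0.60, power 0.80 and alpha 0.05. A two-sided two-sample t test (1:1 allocation assumed) needs 45 per arm, 90 in total. With 50 per arm the power is 0.84. So 100 is sufficient, although the stated inputs do not yield it exactly.

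**Inputs.** From the Protocol: N=100, d=0.60, alpha 0.05, and SD 10 (its STAI example), so the effect is 6.0 points. Power depends only on d, so the scale does not matter. Assumed, because the documents give no value: 50 per arm, complete data, compound symmetry with within-patient correlation rho=0.3/0.5/0.7, two-sided tests, no multiplicity correction, equal visit weights. Write V = (2/50) x 10² = 4.

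**Two main time courses.** Sustained: 0 at admission, 6.0 at all five follow-up visits. Rising: 0, 1.2, 2.4, 3.6, 4.8, 6.0 by visit, which is plausible because in the ICare arm "the remaining steps will be covered at follow-up visits with the physician".

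**Formulas.**
- Six-visit main effect, no covariate: expected value 5 x 6.0/6 = 5.0 (sustained) or 18/6 = 3.0 (rising); variance V(1+5rho)/6, 98 df. SE 1.29/1.53/1.73.
- Follow-up average adjusted for admission: expected value 6.0 or 18/5 = 3.6; variance V[(1+4rho)/5 - rho²](1+1/96), 97 df. SE 1.19/1.19/1.04.
- Month 12 adjusted for admission: expected value 6.0 in both; variance V(1-rho²)(1+1/96), 97 df. SE 1.92/1.74/1.44.
- Treatment x time: noncentrality = sum of squared deviations of the visit effects from their mean, divided by V(1-rho). F with 5 and 490 df if admission is an outcome, 4 and 392 df if only follow-up visits are. Sustained effect with admission in: 30/[4(1-rho)] = 10.7/15/25. Sustained effect with admission out: 0.

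| Power at rho 0.3/0.5/0.7 | Sustained | Rising by visit |
|---|---|---|
| Six-visit main effect, no covariate | 0.97/0.90/0.82 | 0.63/0.49/0.40 |
| Treatment x time, admission an outcome | 0.71/0.86/0.98 | 0.62/0.79/0.96 |
| Treatment x time, follow-up visits only | 0.05/0.05/0.05 | 0.40/0.55/0.80 |
| Adjusted follow-up average | at least 0.998 | 0.85/0.85/0.93 |
| Adjusted month-12 difference | 0.87/0.93/0.985 | 0.87/0.93/0.985 |

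For a sustained effect, the six-visit main effect falls below 0.80 only when rho exceeds 0.74.

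**Admission in both roles.** The six-visit mean is (admission + 5 x follow-up mean)/6. After regression on admission, both the arm coefficient and its SE are 5/6 of those for the adjusted follow-up average, so the test statistic is the same. Simulation (4000 trials per rho) gives estimates of about 5.0 and power of at least 0.998. The estimate is diluted, but the test loses no power.

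**Calendar time.** If the effect rises linearly over weeks 0, 2, 6, 12, 26 and 52 to 6.0, the expected follow-up average is 6.0 x (2+6+12+26+52)/(5 x 52) = 2.26, and its power is 0.47/0.47/0.57. The month-12 figures do not change. A slope-by-treatment test for a sustained effect has power 0.57/0.72/0.90 with equally spaced visits but 0.26/0.35/0.52 on calendar weeks.

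**The case against.** The precision loss needs two conditions: the SAP model without a baseline covariate, and its main effect read as the result. The documents do not favour that reading, because the interaction is the only effect they interpret, and with admission as an outcome it is not diluted. This stands, so the loss is conditional.

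A reader might infer that the two roles together cost power, or that the trial is underpowered. Neither follows. With admission in both roles the test is unaffected. For a sustained d=0.60 effect, even the six-visit main effect keeps 0.80 up to rho of about 0.7. The comparison with 0.80 is itself approximate, because the plan promises multiplicity corrections that it does not specify.

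A reader might also infer that keeping admission as an outcome is an error. It is not: with a common admission mean across arms it is close to equivalent to covariate adjustment.

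Finally, one might answer that the Sample Size section governs. The SAP does not contain it, and it names no deciding contrast either. The strongest objection concerns the remedy: moving admission out of the outcomes while the interaction stays decisive would make matters worse. That is correct, and the fix must deal with it.

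**Conclusion.** The point holds as an unresolved conflict over the role of admission, together with a missing deciding contrast. The one interpreted test, treatment x time, is not tied to the hypothesised better level after treatment.

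Under the stated assumptions and a sustained effect, the defensible readings range from power 0.05 (interaction, admission a covariate only) to at least 0.998 (adjusted follow-up average). The SAP main effect reports 5/6 of the effect. No contrast is best under every time course, so the choice has to be made in advance.

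The sizes rest on assumed correlations, complete data and unadjusted alpha. Use of admission as a baseline also assumes that it is measured before any programme contact. The Protocol says "After the informed consent process, facilitator will open the randomization envelope" and "At study entry, all patients will be asked to complete surveys with a Facilitator", but does not give the order of these two steps.

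This should be fixed. It does not show that the planned power is missed.

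**What to change.** In both documents:

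- Give admission one role. Either use it as a covariate, with its interaction with time, and take outcomes at weeks 2, 6 and 12 and months 6 and 12; or keep it as an outcome with a common mean across arms. The second option retains patients who lack an admission or a follow-up score. If 10% lack each (assumed, at random), the SE of the average is 1.26/1.28/1.14, against 1.33/1.33/1.17 for the covariate form.
- Name one deciding between-arm contrast for Aims 1 and 2, either the adjusted follow-up average or one stated visit such as month 12, and state the expected time course.
- Make treatment x time and the Preacher step secondary. Report every adjusted per-visit difference with a 95% CI, whether or not the interaction is significant.
- Change 3 weeks to 12 weeks in the time-point list.
- Model range of motion over the follow-up visits without a baseline term.

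The cost is wording only, but there are trade-offs. With follow-up outcomes only, treatment x time loses power (0.05 for a sustained effect; 0.40/0.55/0.80 against 0.62/0.79/0.96 for one rising by visit), so it cannot remain the deciding test. The average is weak if the effect grows late. A month-12 contrast loses power with dropout: for a 6.0-point effect and data missing at random after month 6, power is 0.80/0.88/0.97 if 20% lack month 12 and 0.69/0.79/0.93 if 40% do.
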